#### **Study Sessions**

All participants are required to have a BAC of 0.02% or less to complete all study sessions. Each weekly study session will be approximately 60 to 90 minutes in duration, with the exception of session 1 and post treatment, which are expected to last for approximately 3 to 4 hours.

## **Follow-up Period**

One month following completion of study treatment, participants will be asked to complete the 1-month in-person follow-up assessment. Six months after the completion of the study termination, participants will complete the 6-month in-person follow-up assessment. During the follow-up interview, the subject will provide data for the Alcohol Timeline Follow-Back (TLFB), ADIS, SIGH-A and SIGH-D, the self-report battery, and Treatment Involvement Form (TIF). The RA will administer the breathalyzer, TLFB and the TIF. The IE will conduct the ADIS, SIGH-A and SIGH-D, and the CGI-I and CGI-S on Qualtrics. Self-reports will be completed by the participant on Qualtrics.

# **Study Procedures**

Participants will receive 16 treatment sessions over a period of 16 to 21 weeks for UP or 12 treatment sessions in 12 to 16 weeks for TC. Follow-up data will be collected 1- and 6-months post-treatment at in-clinic sessions.

We will offer parking vouchers to participants, as needed, to help defray any costs they may otherwise incur while traveling to our center to complete scheduled assessment appointments. Research personnel will provide up to four parking vouchers (which cost approximately \$10.00 each) to every participant for completion of study assessments.

Note: As of March 18th, 2020, study staff adapted study procedures to operate remotely during the COVID-19 pandemic. These practices have continued into 2021, 2022, 2023, and the remainder of the study. This has included instituting procedures to conduct therapy sessions via telehealth (HIPAA Zoom), collecting data remotely via online services (Qualtrics, Millisecond), and conducting screenings remotely (HIPAA Zoom). IRB approval was obtained for all remote procedures. fMRI procedures were temporarily discontinued due to the COVID-19 pandemic in 2020, but study staff re-initiated scans in 2021 in accordance with BU IRB protocols.

## **Ecological Momentary Assessment (EMA)**

The EMA component is required by all participants, unless an exception is made by the project director, [name]. The Ecological Momentary Assessment (EMA) component will collect self-reported drinking data in real time using a smartphone app, *RealLife Exp*. RealLife Exp will send timed alerts 3-times a day at 10am, 4pm and 10pm to study participants. In addition to the scheduled EMA assessments, participants will have the option to self-initiate the survey during a drinking episode if they choose to do so. We will activate the EMA component for 5 weeks for the UP condition (1, 4, 8, 12, 16), and 4 weeks for the control condition (1, 4, 8, 12) over the course of treatment. Participants will be instructed to complete EMA for the full time period starting from the session it was activated, to when they come in for their next session, with the exception of the baseline EMA. The RA should activate EMA on the screening session, session 3, 5, 7, and 15, and deactivate EMA on session 4, 8, 12, and 16. The baseline EMA should be collected starting from screening session, and deactivated 7-days later regardless of when session 1 is scheduled.

To "activate" the survey, the RA should search for "StAR2" in the download survey section in RealLife Exp, click download, and enter in the access code ("star") when promoted. After the week of EMA has been completed, the RA should assist the participant in deactivating the survey, by swiping the downloaded StAR2 pack to the left and then pressing the trash icon.

A copy of these instructions

will also be handed out to the participant at their screening session.

A smart phone (with limited functionality) will be provided to participants who do not own one themselves. The phone will be returned to study staff once participants have completed the study. Each participant will be assigned a dummy email address which will not include any identifiable information. Assigning dummy emails to the participants resolves the issue of having protected health information linked to identifiable information in any way. The list of dummy email addresses can be found at:

Once an email has been assigned to a participant, the RA must update the list with the participants' ID next to the email they were assigned.

After each participant finishes their last course of EMA (on their last session), the RA will permanently delete access to the EMA survey based on their participant ID. This will prevent the participants from attempting to continue participating in EMA after treatment has completed. The RA will also determine if the participant completed at least 80% of the EMA component. If they completed 80% or more of the EMA, they should be paid \$50.

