#### **Scheduling/Tracking Sessions**

The RA schedules the first treatment session with the participant after the Screening Session appointment via phone once the full team consensus meeting has been held to determine participant eligibility. Once the participant is determined to be eligible, the RA determines randomization to treatment condition.

Only RAs, and the PI will have access to the randomization list. The RA should add participants to the list by ID number in chronological order. Next the RA should ask [name] which therapist the participant has been assigned to. The participant should be scheduled for session 1 as soon as possible to ensure a definite start date within the first month after the screening session.

Throughout the active treatment phase, the therapist is responsible for scheduling treatment sessions with participants, and informing the RA of the treatment schedule and time of upcoming appointments (via email). When discussing the date and time of the next appointment with the patient, the therapist should also build in time for the RA portion of the assessment (e.g., an additional 30 or 45 minutes before the therapy session, depending on session number).

Therapy sessions are 50 minutes for UP participants and 30 minutes for TC participants. A urine sample will need to be collected by [name] or a trained RA on the screening session, MRI sessions, sessions 1, 4, 8, 12, and 16 (if applicable; for UP condition only). A blood sample will be collected by the study nurse on the screening and last treatment session. On session 1 and the last treatment session (12 for TC; 16 for UP) the RAs will need approximately 2 hours total to complete their portion of the session. Please see the table below for breakdown of how long to schedule each session for.

Note: As of March 18th, 2020, due to remote procedures, urine and blood sample collection has been reduced to the screening session and post-assessment only (after the last treatment session), at a Quest Diagnostics facility. A urine sample for pregnancy and drug testing is still collected in-person when a participant comes in for an fMRI.

Session #	Time for Medical	Time with Therapist Time with RA		Time for IE
Baseline	30 min	N/A	1.5 hours	2 hours
Session 1	15 min	50 min UP, 30 min TC	1 hour & 45 min	N/A
Session 2	N/A	50 min UP, 30 min TC	30 min	N/A
Session 3	N/A	50 min UP, 30 min TC	30 min	N/A
Session 4	15 min	50 min UP, 30 min TC	30 min	N/A

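### The EMA switch-on list does not match the planned EMA weeks: followed as written, week 12 is skipped in both arms and Take Control has no end-of-treatment EMA

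*Combined protocol and SAP*

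**What the plan says.** All the conflicting statements are in the section Ecological Momentary Assessment (EMA).

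- **Planned weeks, UP:** "We will activate the EMA component for 5 weeks for the UP condition (1, 4, 8, 12, 16".
- **Planned weeks, TC:** "4 weeks for the control condition (1, 4, 8, 12) over the course of treatment".
- **Length of a run:** "starting from the session it was activated, to when they come in for their next session, with the exception of the baseline EMA". The baseline run starts at screening and is "deactivated 7-days later regardless of when session 1 is scheduled".
- **Switch-on:** "The RA should activate EMA on the screening session, session 3, 5, 7, and 15".
- **Switch-off:** "deactivate EMA on session 4, 8, 12, and 16".
- **Prompts:** three timed alerts a day, plus optional self-initiated entries.
- **Payment:** "The RA will also determine if the participant completed at least 80% of the EMA component", with $50 paid to those who did.

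The same section says that a participant's final EMA course finishes at the final session. Scheduling/Tracking Sessions fixes which session that is in each arm: "On session 1 and the last treatment session (12 for TC; 16 for UP".

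**The concern.** The planned weeks and the switch-off list agree with each other. The switch-on list agrees with neither. It contains a session 5 that leads to no planned week, and it lacks any session that would open the week closing at session 12.

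This is a step-by-step instruction to research assistants, so faithful compliance is what produces the gap. The gap also falls unequally. Both arms lose week 12, but week 12 is the last treatment week only in TC. UP would still have real-time drinking data at the end of treatment and TC would not, so EMA could not be compared between arms at that point. Prompts would also be sent in a week that nobody planned, and the 80% completion rule could be read against a schedule that was never delivered.

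**Working it through.** This is a reconciliation of lists; no power or error-rate figure is involved.

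**Inputs.** Planned weeks, switch-on list, switch-off list, run-length rule and three prompts a day come from the EMA section. The last sessions (TC 12, UP 16) come from Scheduling/Tracking Sessions.

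**Assumptions.** The screening run is week 1. A run switched on at session s covers the interval to session s + 1 and is labelled week s + 1. This labelling fits the plan's own pairs 3→4, 7→8 and 15→16. Sessions are weekly, so one run is 7 × 3 = 21 prompts. Self-initiated entries are not counted.

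**Step 1: pair the two lists.** Switch-ons 3, 7 and 15 pair with switch-offs 4, 8 and 16. Switch-off 12 has no switch-on at 11. Switch-on 5 has no switch-off at 6.

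**Step 2: try to reproduce the planned weeks, each run ending at the next session as the text states.**

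| Arm | Planned weeks | Weeks from the printed list | Missing | Extra |
|---|---|---|---|---|
| UP | 1, 4, 8, 12, 16 | 1, 4, 6, 8, 16 | 12 | 6 |
| TC | 1, 4, 8, 12 | 1, 4, 6, 8 | 12 | 6 |

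The planned weeks are not reproduced. The number of runs is right (5 in UP, 4 in TC), so a simple count would not reveal the error.

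**Step 3: try the other reading, in which a run continues to the next listed switch-off.** The session 5 run then lasts to session 8 and absorbs the session 7 run. The intervals covered after screening are 3–4, 5–6, 6–7, 7–8 and, in UP, 15–16. Interval 11–12 is still off in both arms.

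**Step 4: prompts deliverable inside the planned weeks.**

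- UP: planned 5 × 21 = 105; deliverable (weeks 1, 4, 8, 16) 4 × 21 = 84; 84/105 = 80%.
- TC: planned 4 × 21 = 84; deliverable (weeks 1, 4, 8) 3 × 21 = 63; 63/84 = 75%.

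**Step 5: off-plan prompts from session 5.** If the run ends at session 6, the excess is 1 × 21 = 21. If it lasts to session 8, it covers three intervals, but 7–8 is planned week 8, so the excess is 2 × 21 = 42.

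**Step 6: check the correction.** Switching on at screening and sessions 3, 7, 11 and 15 gives weeks 1, 4, 8, 12, 16 in UP. Without session 15 it gives 1, 4, 8, 12 in TC. Both match the plan, and each switch-on after screening pairs with one switch-off.

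**The case against.** The strongest reply is that this is a clerical slip of little analytic consequence. The planned weeks, the switch-off list and the statement that the last course ends at the last session all point to the same intended schedule, so one number in a staff instruction looks wrong. The documents do not show what was actually switched on. That stands as a limit on what can be claimed about the data collected. It does not repair the text: no other section supplies a session 11 switch-on.

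Three stronger readings are tempting, and the documents do not support them.

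- **That the trial loses its check on reported drinking at the end of treatment in TC.** No section plans to check the Timeline Follow-Back against EMA. EMA does not appear in the data analysis aims, the fMRI aims or the primary hypotheses. Daily drinking comes from the Timeline Follow-Back at every treatment session. The assessment schedule places PEth and EtG at the last treatment session in both arms, and the remote procedures kept blood and urine collection after that session.
- **That no TC participant could earn the EMA payment.** This needs the denominator to be the planned weeks and the session 5 prompts to be discarded. The denominator is not stated. If it is the prompts from the printed list under the next-session rule, the totals are 105 in UP and 84 in TC, and full completion is possible in both arms.
- **That session 5 adds three off-plan weeks (3 × 21 = 63 prompts).** This counts planned week 8 as unplanned and sets aside the stated rule that a run ends at the next session.

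**Conclusion.** The EMA section contradicts itself, and the contradiction holds on either reading of run length. Followed as written, week 12 is activated in neither arm. TC has no EMA after session 8 and none at the end of treatment, while UP keeps week 16.

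The prompt figures in the working assume weekly sessions. The plan allows 16 to 21 weeks for UP and 12 to 16 for TC, so actual run lengths may differ. The effect on payment is conditional: on a planned-weeks denominator, a fully compliant TC participant reaches at most 75% and a UP participant exactly 80%; on a delivered-prompts denominator there is no effect.

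The consequence is confined to the EMA data. The correction is worth making because the instruction governs what staff collect and the loss differs by arm, but the primary and listed secondary outcomes do not rest on it.

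**What to change.** - **Correct the list.** Replace the switch-on sessions with screening and sessions 3, 7, 11 and, in UP only, 15. The switch-off list can stay as it is.
- **Name the denominator** of the 80% rule in the same edit, so that payment does not depend on which schedule a reader has in mind.
- **Participants already treated.** The Study Procedures section describes remote work continuing through 2023, so some EMA data may already have been collected under the printed list. Check the activation records and report which EMA weeks were captured, by arm. Make no between-arm comparison of end-of-treatment EMA where TC week 12 was not collected.

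**Cost.** One or two sentences in the manual, submitted as an amendment under the manual's own rule for protocol changes, plus one pass through the activation records. Participants complete no more EMA weeks than already planned. The edit cannot recover week 12 runs already missed, which is why the records check is needed.

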#### fMRI

Participants that are selected for the fMRI component will also be screened for eligibility in undergoing brain fMRI scans after completing the assessment session at CARD. All enrolled participants must be willing and able to participate in the fMRI component in order to be eligible

to participate in the trial, unless an exception is made by the project director, [name]. About half of the eligible participants randomized to the UP condition will be asked to complete this component of the trial. We will ask all participants in the UP condition to complete the fMRI component until we have reached a sufficient number of participants (with complete scans) to evaluate the fMRI specific aims identified in the approved study protocol.

One scan will occur after randomization but before the first treatment session begins and the second scan will occur within 2 weeks after the last treatment session. Participants will be screened before each scan session for alcohol use (breathalyzers), pregnancy (urine sample, women of childbearing potential only), and illicit substance use (urine sample). Eligible participants may be asked to complete 2 fMRI sessions of 2 hours total. Thirty minutes will be allocated for BAC, pregnancy test (urine sample; women of childbearing potential only), illicit substance use test (urine sample), Alcohol Use Questionnaire (AUQ), and the CILSE safety form. Thirty minutes will be allocated for traveling to CILSE, and prepping materials for the MRI, and 1-hour and a half will be used for the 3 Tesla fMRI scan involving structural imaging (MRI) and functional imaging (fMRI). The participant should complete the AUQ both before and after the fMRI scans in Qualtrics.

The fMRI scans include a resting-state scan (no task involved), a cognitive (Stroop) task, an alcohol cue reactivity task and an Event Based Reappraisal Task. The Stroop, alcohol cue, and Event Based Reappraisal scans involve presentation of visual images to participants while they are in the scanner. No contrast agent or invasive procedures are used. Only personnel trained in working in high magnetic field environments will work on this project. Imaging data will be analyzed on secure networks using only encrypted files. All data obtained will be coded to protect participants' privacy and confidentiality.

If a participant is struggling with claustrophobia while in the scanner, the following procedures are in place: stop the task and call [name] **Continue**, the project director, for guidance on whether to continue with the fMRI. If [name] is unavailable, call the postdoctoral fellow, **Continue** the MRI consultant. All of these phone numbers are also saved in the study phone. Signs that the participant is struggling with claustrophobia include needing an RA to stay inside the scanner room during the scan, needing frequent breaks, and/or verbally indicating they are feeling claustrophobic or want to get out.

#### **MRI Instructions for RAs**

Two RAs will accompany participants to the Center for Integrated Life Sciences and Engineering (CILSE) located at [name]. All RAs involved in MRI visits are required to complete the Level 1 MRI safety training and quiz.

Before leaving CARD the RA must:

• Administer the MRI CLISE safety screening form to the participant. This form is located in the participant's binder (MRI 1 and MRI 2 tabs)

- Administer the AUQ self-report questionnaire before and after the MRI scan
- Remember to bring the study laptop, charger, BU ID, and Eprime case (with license key)

# **Instructions for Scanner Room for RAs**

## Before Entering the Scanner Room:

Note: The screening form must be reviewed by a CILSE/MRI staff member in order for the participant to complete the scan.

- Make sure the linens on the scanner bed and pillow are new and clean
- Have the participant change into scrubs
- Ask the participant to remove ALL metal items (e.g., jewelry, belts, watches, credit cards). Lockers are provided for storage of clothing and personal items
- Use the metal detector wand and scan the participant's body for any metal that may have been missed
- The RA must remove all metal items from his/her own body

# Familiarize the Participant with the Button Box:

One RA will bring the participant into the scanner room, while the other RA prepares the Eprime tasks with the MRI technician. The RA who accompanies the participant into the scanner room will familiarize the subject with the button box.

- Make sure the participant is using the button box that is labeled (R, G, Y B)
- Explain how to use the button box, as follows:

"Please hold the button box vertically, with your dominant hand on top. Use the index and middle fingers of your dominant hand for the top two buttons, and the index and middle finger of your non-dominant hand for the last two buttons."

- Demonstrate how the participant should hold the box and where they should place their fingers when explaining
- Explain the order of the colors in relation to the location of the wire

# Example Dialogue:

"The blue button is closest to the wire, then yellow, then green, and then red. Red is the button furthest from the wire."

• Obtain verbal confirmation that the participant understands how to hold and use the button box

Warn Participants of Loud Noises During the Scan and Provide Ear Protection:

• Warn participants again about the loud noises that will occur during the scan

- Provide the participants ear protection and instruct them on how to use it. The RA should show the participant how to roll and squeeze the ear plugs in their hand and insert them into their ears
- Confirm with the participant that the ear plugs are fully inserted and fully functional

Familiarize the Participant with the Squeeze Ball:

- Lower the scanner bed and help the participant climb on
- Inform the participant that there is an intercom that will allow research staff to talk to him/her, and that staff will be checking in periodically
- Hand the participant the button box
- Place the squeeze ball on the participant's chest and explain its function

# Example Dialogue:

"I am placing a squeeze ball on your chest. If at any time during the scan you feel like you have to stop and exit the scanner, squeeze it and a loud noise will alert us outside that we need to stop the scan and check on you."

• Receive verbal confirmation the participant understands the function and usage of the squeeze ball

Reminders for the Participant

- Inform the participant again that during the first few minutes of the scan there is a small possibility they will experience peripheral nerve stimulation
- Remind the participant to try and stay extremely still for the duration of the scan
- Remind the participant to stay awake for the duration of the scan

Aligning the Head Coil

- Insert foam pads in the empty space around the participant's head in order to minimize movement during the scan
- Place the foam leg cushion underneath the participant's knees for comfort
- Retrieve the head coil and carefully place it over the participant's head; during this time please be mindful of the participant's comfort
- Raise the bed and adjust the mirror. The participants should be able to see straight back
- Tell the participant to close his/her eyes and keep them closed. Turn on the aligning laser and line up the red laser line with the white line on the head coil
- Turn off the laser and tell the participant it is now safe to open his/her eyes
- Receive verbal confirmation that the participant is comfortable and believe this will be a comfortable position for the next hour.
- Inform the participant that the bed will now be sent into the scanner

• Once the participant is fully in the scanner inform him/her that you are now exiting the room and closing the door, but you will be able to communicate through the intercom

# Resting State Scan:

- Once the RA has left the participant in the scanner room, he/she must turn on the intercom and inquire about the participant's comfort. Wait for a response in order to continue
- Inquire about the positioning of the monitor screen. Fix the mirror/screen as needed
- Inform the participant that now the screen will go black for a short time. During this time, the resting state scan will take place. It will take approximately 10 minutes to complete. Remind the participant to remain awake and stay as still as possible

# Example Dialogue:

"Hi X, how are you doing? Are you comfortable? Can you see the screen ok? Good. We are going to start in just a few minutes and you will hear those loud noises we talked about earlier. For right now the screen is going to go black as we collect some initial data and it will come back on for the tasks. Right now, we ask that you remain awake, with your eyes open and try not to think about anything in particular. Remember to stay as still as possible. This will take about 10 minutes to complete."

